**Table 2 Study Disposition of Enrolled Patients with Incomplete Data for Primary Analysis**

Reason study data are incomplete	Full Analysis Set?	Safety Analysis Set?	Notes
Withdrawal prior to administration of IV  Zr-TLX250	No	No	Replace (All subsequent categories assume administration of IV  Zr-TLX250 occurred)
Withdrawal before PET/CT imaging	No	Yes	
PET/CT images cannot be analysed due to technical failure	No	Yes	eCRF to document technical failures
Incorrect enrolment (did not meet the required inclusion/exclusion criteria)	No	Yes	
Patient withdrawal for reasons not related to disease (pregnancy, noncompliance, etc.)	No	Yes	See section 4.3.2
Evidence of N1 or M1 disease on  Zr-TLX250 PET/CT imaging, leading to additional staging and/or change in treatment strategy.	Yes	Yes	Histopathologic determination of any lesion (primary renal or metastatic) will be taken as standard of truth
No evidence of N1 or M1 disease, and nephrectomy material not available for evaluation of presence or absence of ccRCC - for example if surgery is performed and no tissue is removed for assessment.	No	Yes	eCRF to document reasons

Sample size determination is based on the Full Analysis Set.

All patients in the Safety Analysis Set will complete final study visit procedures following withdrawal or study completion.

Patients who have received study drug and are withdrawn due to an AE related to the study drug will be included in the safety analysis.

Patients who received study PET imaging, but do not have adequate surgical material to analyse may be followed-up by further imaging at the discretion of the investigator, in the best interest of the patient.

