### 8.3 Determination of Histological Standard of Truth

Partial and total nephrectomy are routinely used in the management of cT1 renal tumours.

All patients enrolled in the study will already be scheduled for partial nephrectomy or total nephrectomy as part of standard work-up and management of an indeterminate renal mass.

A small number of patients may be found to have an extra-renal focus of increased radioactivity accumulation that is suspicious for metastatic disease. In these patients, the investigator may elect to undertake further diagnostic work-up including additional imaging, which may result in a change in surgical strategy. Results of the PET scans should not dictate clinical management.

If results of further standard workup confirm metastatic disease, then biopsy might be performed. Biopsy results will be considered in the exploratory analysis (See Section 9.1.2.7).

The resected lesion will be localised by the site surgeon or pathologist using the localisation scheme in 8.1.4 above. The independent image readers will not have access to this evaluation.

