#### 8.3.2 Independent Central Pathologist

Representative, non-stained but paraffin-embedded slides of lesion tissue (N=15) will be sent to a central pathology service as contracted by the Sponsor. The procedures for preparation, labelling and shipment of these representative slides from the local pathologists to the central pathologist will be described in a separate Pathology Manual to be provided to the local pathologists.

The primary purpose of the independent histopathology review is the determination of the histological diagnosis of the renal mass (ccRCC or non-ccRCC) as the standard of truth for comparison with Zr-TLX250 imaging.

For patients in whom unexpected evidence of disseminated disease has been observed, any available tissue samples from biopsies of extrarenal lesions will also be analysed centrally.

Details of the central evaluation procedure are described in a separate document prepared by the central pathology service.

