### 9.1.2.7 Exploratory Variables

In situ biological half life of girentuximab protein in tumour lesions will be estimated, using a general model of average girentuximab kinetics in tumour tissue, derived from serial Zr-TLX250 imaging. Based on (a) protein residence times in the lesions, (b) an assumed specific activity of therapeutic labelling with Lutetium-177 (Lu), and (c) the measured tumour lesion volume (CT dimensions), an achievable therapeutic absorbed dose to tumour (Gy), will be determined for several specific activities and hypothetical activity doses of Lu.

Exploratory analyses will be delineated in more detail in the Statistical Analysis Plan (SAP) prior to analysis including extra-renal lesions used as a histology standard of truth (when N1 or M1 disseminated disease is suspected)

Additional exploratory investigations correlating the Zr-TLX250 tumour lesion SUVs, semi-quantitation of CAIX expression as determined by immunohistochemistry, and evaluation of the distant masses outside the kidney identified on Zr-TLX250 whole body PET/CT in patients with unexpected evidence of disseminated disease will be conducted.

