### 9.2.1 General Considerations

The aim of this study is to evaluate sensitivity, specificity, PPV, NPV, as well as accuracy of Zr-TLX250 PET/CT imaging using a 37 MBq (1 mCi) activity dose to detect ccRCC in patients with IRM of stage cT1, and who are scheduled for partial or total nephrectomy.

Histological confirmation from nephrectomy (or biopsies of extrarenal lesions from patients in whom unexpected evidence of disseminated disease is observed) will serve as standard of truth. The qualitative Zr-TLX250 PET/CT imaging assessments of 3 independent readers will be the primary imaging result.

All data will be listed and trial summary tables will be provided. Descriptive statistics will be presented. Secondary variables will be summarized. The statistical evaluation will be performed by using SAS® statistical software (version 9.4, or higher).

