### 9.2.2 Analysis Sets

The Full Analysis Set (FAS) will consist of all enrolled patients who have evaluable PET/CT imaging and have a confirmed histopathology diagnosis (Table 2).

The Safety Analysis Set (SAF) will consist of all patients who received Zr-TLX250.

The Screening Analysis Set (for CONSORT-style accounting of subject disposition) will consist of all patients assigned a Patient Number (section 4.4).

All primary and secondary efficacy analyses will be carried out using the FAS.

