8.1 Full Analysis Set

The Full Analysis Set (FAS) will consist of all enrolled patients who have evaluable PET/CT imaging and have a confirmed histopathology diagnosis.

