9.2.7 Exploratory Variables

In situ biological half-life of girentuximab protein in tumour lesions will be estimated, using a general model of average girentuximab kinetics in tumour tissue, derived from serial ⁸⁹Zr-TLX250 imaging. Based on (a) protein residence times in the lesions, (b) an assumed specific activity of therapeutic labelling with Lutetium-177 (¹⁷⁷Lu), and (c) the measured tumour lesion volume (CT dimensions), an achievable therapeutic absorbed dose to tumour (Gy), will be determined for several specific activities and hypothetical activity doses of ¹⁷⁷Lu.

Exploratory analyses will include Extra-renal lesions used as a histology standard of truth (when N1 or M1 disseminated disease is suspected) along with investigations correlating the ⁸⁹Zr-TLX250 tumour lesion SUVs, semi-quantitation of CAIX expression as determined by immunohistochemistry, and evaluation of the distant masses outside the kidney identified on ⁸⁹Zr-TLX250 whole body PET/CT in patients with unexpected evidence of disseminated disease will be conducted.

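### Protocol Table 2 and Section 8.3 disagree on whether extra-renal histology can be the standard of truth in the co-primary analysis, and the SAP does not settle it

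*Protocol*

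**What the plan says.** **Wording that brings extra-renal histology into the primary analysis.** Protocol 4.3.3, Table 2, has a row for patients with N1 or M1 on the study PET/CT, where that finding led to further staging or an altered treatment strategy. They are marked as in the FAS, with the note "Histopathologic determination of any lesion (primary renal or metastatic) will be taken as standard of truth". Protocol 9.2.2 refers to Table 2 in defining the FAS and runs all primary and secondary efficacy analyses on it. Protocol 9.2.1 says that nephrectomy histology "or biopsies of extrarenal lesions from patients in whom unexpected evidence of disseminated disease is observed) will serve as standard of truth". SAP 10.1 repeats this.

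**Wording that points elsewhere.** Protocol 8.3, on patients with confirmed metastatic disease, says: "Biopsy results will be considered in the exploratory analysis (See Section 9.1.2.7". Protocol 8.3.2 gives the main purpose of central pathology as "determination of the histological diagnosis of the renal mass (ccRCC or non-ccRCC) as the standard of truth". Protocol 9.1.2.7 lists extra-renal truth among exploratory analyses, and SAP 9.2.7 says: "Exploratory analyses will include Extra-renal lesions used as a histology standard of truth (when N1 or M1 disseminated disease is suspected".

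**The SAP's analysis set.** SAP 8.1 takes "all enrolled patients who have evaluable PET/CT imaging and have a confirmed histopathology diagnosis". It does not say which lesion, and the SAP has no counterpart to Table 2. SAP 8.3 runs all efficacy analyses on this set.

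**The PET read.** Protocol 9.1.1 and SAP 9.1 build the co-primary 2x2 table on uptake in the target lesion. Protocol 8.2.2.1 also calls a scan positive if at least one tumour lesion is positive.

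**The concern.** The 2x2 table needs a histology result and a PET result for the same object. For this group of patients the protocol gives two answers on the histology, and two candidate reads that could go with it. The case can arise, because Protocol 7.5 allows a biopsy of an accessible extra-renal lesion in place of the nephrectomy.

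Two things are at stake. First, whether the patient is in the primary table at all. Second, whether metastatic histology is set against a read of the renal mass, which would count agreement or disagreement between two different lesions as diagnostic performance. If the choice is left until reads and histology are linked, its effect on the result will be visible when it is made.

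**Working it through.** The plan states no figure on this point. The check is a comparison of texts, followed by a calculation of how much one patient can matter.

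**1. Cells reached under the stated rules**

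| Patient (only the extra-renal focus is biopsied) | Target-lesion read | Scan-level read | Exploratory only |
|---|---|---|---|
| Renal mass read negative, focus positive, biopsy ccRCC | FN | TP | absent |
| Renal mass read negative, focus positive, biopsy non-ccRCC | TN | FP | absent |
| Both read positive, biopsy ccRCC | TP | TP | absent |
| Both read positive, biopsy non-ccRCC | FP | FP | absent |

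In the third row the only question is TP or excluded. A patient with both tissues and discordant histology has no assigned truth, because no supplied passage gives precedence.

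**2. Assumed class sizes.** From Protocol 9.3.1 and SAP 7: 70% cT1a with 34% non-ccRCC, and 30% cT1b with 17%. The non-ccRCC share is 0.70 × 0.34 + 0.30 × 0.17 = 0.289.
- N = 252 (protocol): 252 × 0.289 = 72.8, so 73 non-ccRCC and 179 ccRCC.
- N = 300 (SAP 5.1 and 6): 300 × 0.289 = 86.7, so 87 and 213.

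**3. Pass marks per reader.** The Wilson lower bound is L = [p + z²/2n − z√(p(1−p)/n + z²/4n²)] / (1 + z²/n), with z = 1.96. L must exceed 0.70 (sensitivity) or 0.68 (specificity).

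| Endpoint, N | Lowest passing result | One patient added as error | One added as correct |
|---|---|---|---|
| Sensitivity, 252 | 138/179: 0.7041 | 138/180: 0.6997, fails | 139/180: 0.7056 |
| Specificity, 252 | 58/73: 0.6883 | 58/74: 0.6773, fails | 59/74: 0.6921 |
| Sensitivity, 300 | 163/213: 0.7040 | 163/214: 0.7003, passes | – |
| Specificity, 300 | 68/87: 0.6839 | 68/88: 0.6749, fails | – |

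**4. Chance that the extra patient matters.** The true value is taken as 0.83, the planning value. One added error removes the pass only for a reader who lands exactly on the pass mark. The binomial probabilities are 0.0843 (58 of 73), 0.0525 (68 of 87) and 0.0092 (138 of 179). For sensitivity at N = 300 one added FN never removes a pass.

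**5. At least two of three readers.** With independent readers who each pass with probability q, the chance is 3q²(1−q) + q³. With identical readers it is q. Each endpoint is taken alone.

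| Added for all three readers | q before → after | Independent readers | Drop, independent to identical |
|---|---|---|---|
| FP, 73 negatives | 0.8332 → 0.7488 | 0.9258 → 0.8425 | 8.3 to 8.4 points |
| FP, 87 negatives | 0.9072 → 0.8547 | 0.9758 → 0.9428 | 3.3 to 5.2 points |
| FN, 179 positives | 0.9835 → 0.9743 | 0.9992 → 0.9980 | 0.1 to 0.9 points |
| FN, 213 positives | no change | no change | 0 |

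**The case against.** The best reply is that most of these passages can be read together. Protocol 9.1.2.7 and SAP 9.2.7 list extra-renal lesions among exploratory analyses but do not rule out primary use. Protocol 9.2.1 names neither the FAS nor any lesion; that link comes from Table 2 through 9.2.2. The Table 2 row is conditional, so it does not cover every patient with N1 or M1 on PET. The synopsis and SAP 10.2.1 define patients whose surgical material cannot be assessed as drop-outs, but Protocol 8.3.1 uses the term surgical material for extra-renal tissue too, so that wording does not clearly remove them. The target lesion is the one delineated on pre-baseline imaging, and entry requires a single mass confined to the kidney, so only the scan-level sentence competes with it. The plan states no pairing of a metastasis with its own read in the co-primary table. The image review charter and the central pathology document were not supplied and may fix pairing and precedence.

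All of this narrows the point. What stands is that Table 2, through the FAS definition, puts any-lesion histology into the primary analysis, while 8.3 assigns biopsy results to the exploratory analysis and 8.3.2 defines truth by the renal mass. No passage states that both uses are intended. Even if they are, any-lesion histology against a target-lesion read would compare different lesions.

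**Conclusion.** The conflict is in the current text, and the SAP does not resolve it. It should be fixed, but its reach is limited to patients with extra-renal tissue and no renal specimen, or with discordant histology. Protocol 8.3 speaks of a small number with extra-renal foci and gives no figure.

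The size is conditional on one such patient existing and being scored as an error by all three readers. At a true specificity of 0.83, the chance that at least two readers pass specificity falls by about 8 points (73 negatives assumed) or 3 to 5 points (87 assumed). For sensitivity the loss is under 1 point. The unconditional effect is smaller, and it matters only near a threshold.

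A reader might infer that the any-lesion rule inflates sensitivity. The documents do not support a direction: the same patient can be TP, FN or absent, or FP, TN or absent, depending on the read used and the biopsy result. A reader might also infer that exclusion is the only defensible choice. That does not follow, since Table 2 makes an explicit decision to include. Either option can be defended if the pairing is fixed in advance.

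**What to change.** Before reads are linked to histology, reconcile Protocol Table 2, 8.3, 9.1.2.7, 9.2.1, 9.2.2 and the synopsis drop-out wording with SAP 8.1, 8.3, 9.2.7, 10.1 and 10.2.1. SAP 8.1 and 8.3 must be included, because they would otherwise still admit patients with only extra-renal histology to the primary analysis. The text should state:

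- The co-primary 2x2 table never pairs the read of one lesion with the histology of another.
- Central histology of the renal mass, paired with the reader's call on that mass, takes precedence whenever it exists.
- Patients with only extra-renal histology are either in or out of the primary table, under one rule, and their number is reported.
- The other option is a sensitivity analysis per reader. It uses the read of the biopsied lesion where one exists and lists patients for whom none does. Such gaps are possible: Protocol 7.5 refers to the most accessible lesion, while 8.2.2.5 has only the two largest non-target lesions per organ evaluated.

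Check that the image review charter and the central pathology document use the same pairing and precedence.

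The cost is wording in two documents and one sensitivity analysis. If these patients are left out, a few leave the primary table and that exclusion depends on the index test; the sensitivity analysis shows its effect. Clinical management is not affected.

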#### **4.4 Patient Identification**

All patients who attend a screening visit will be identified by a unique identification number ("Patient Number") that consists of 5 digits in two parts:

- The site number is a 2-digit number that is provided by the sponsor or the ABX-CRO project manager prior to the start of recruitment.
- The screening number is a 3-digit number that is consecutively assigned by the site to each patient after informed consent.

Example: The first patient screened by site "01" will receive patient number 01-001.

Example: The third patient at site "12" will receive patient number 12-003.

The screening number will be assigned at the screening visit by the responsible nuclear medicine service of the study centre, if the initial review of the patient's history/patient interview indicates possible eligibility, and if the informed consent form has been signed by the patient.

Investigational sites are required to keep a patient identification list in the trial master file (TMF) (see also Section 10.4.1), identifying their patients by name, date of birth, patient number and status (screen failure/completed study/withdrawn). This list will be reviewed by assigned monitors, but has to stay on site and will not be collected, in order to protect confidentiality.

## **5 Study Treatment**

### **5.1 Study Drug Zr-TLX250**

#### **5.1.1 Chemical Properties**

Zr-TLX250, is a chimeric monoclonal antibody (INN name: girentuximab) with specificity for the CAIX (carbonic anhydrase 9) antigen, radiolabelled with the positron emitting radio-metal zirconium-89. Girentuximab has a CAS number of 916138-87-9.

The chemical formula, without the Zr and the desferrioxamine, is C6460H1006N1718O2018S48 with a molecular mass of 146.5 kg/mol.

#### **5.1.2 Pharmaceutical Properties**

Zr-TLX250 is formulated as a solution for intravenous administration in glass vials (Europe, Australia, Turkey and Canada) or in a syringe (USA) at the nominal dosage strength 37 MBq (±10%) for single intravenous use. The Zr-TLX250 drug product is manufactured as “ready-to-use”. The composition of Zr-TLX250 solution for IV administration includes the active pharmaceutical ingredient in a buffered solution without other excipients, as described in the investigator’s brochure.

A complete record of batch numbers and expiry dates of all study medication will be maintained in the trial master file (TMF).

#### **5.1.3 Storage and Handling**

The product is to be shipped and stored at room temperature (15°C to 30°C) inside the lead-shielded container provided and protected from light.

The product must be handled within a hospital environment only, by an accredited radiopharmacist and/or nuclear medicine physician according to international and local radiation protection guidelines.

#### **5.1.4 Dosage and Administration**

The mass dose of Zr-TLX250 to be used in this phase 3 study will be 10 mg, labelled with 37 MBq (±10%) Zr per dose.

[figure not shown]
Each patient will receive a single slow intravenous (IV) administration over a minimum of 3 minutes on Day 0 (after pre-dose assessments), at the nuclear medicine service of the respective study site.

No dietary restrictions prior to dosing are necessary.

Please refer to the IMP Handling Manual for a detailed description. In brief, prior to administration, an indwelling intravenous catheter has to be placed into the antecubital vein or an equivalent venous access. Please refer to Figure 1.

**Figure 1 Infusion set with filter**

Intravenous infusion set-up showing 0.22 micrometer filter in-line between syringe and infusion port (for reference only).

The radiopharmaceutical will be slowly administered through the indwelling catheter and followed with a  $\geq 15$  mL saline flush. The syringe will be assayed prior and after administration to assess the injected radioactive dose (MBq).

The dose that will be administered to the individual patient will be assessed using a dosing calibrator as outlined in the IMP Handling Manual.

### 5.1.5 Packaging and Labelling

Zr-TLX250 solution for IV administration will be supplied in glass vials (Europe, Australia, Turkey and Canada) or in a syringe (USA) in appropriate packaging (lead-shielded containers bearing a radioactive warning symbol in accordance with radioactive pharmaceutical requirements). The labels of the packaging supplied by the sponsor will include the following information as a minimum:

- Name and address of sponsor
- Study number
- Name of study drug and formulation
- Dose strength
- Batch number

- Expiry date
- Storage instructions
- Radioactive warning symbol
- “For Clinical Trial Use only”.

All manufacturing, formulation and labelling will be done in accordance with applicable current GMP and local guidelines and laws.

#### **5.1.5.1 Medication Numbering**

A system of medication numbering in accordance with all requirements of Good Manufacturing Practice (GMP) and any applicable regulatory requirement will be used for all study drugs. This will ensure that, for each patient, any dosing of study drug can be identified and traced back to the original bulk ware of the active ingredients.

Lists linking all numbering levels will be maintained by the institutions in charge of study drug packaging.

#### **5.1.6 Drug Logistics and Accountability**

##### **5.1.6.1 Supply, Storage, Dispensation and Return**

Zr-TLX250 solution for IV administration will be manufactured, handled and stored in accordance with GMP. Zr-TLX250 contains radioactive material and should only be handled by personnel trained in the use of radioactive isotopes with proper shielding and monitoring. Receipt and use of Zr-TLX250 is limited to institutions holding an appropriate handling permit by their competent national or regional authority.

All required documentation, e.g. written approval from the independent ethics committee (IEC)/institutional review board (IRB) and regulatory authority, as appropriate, needs to be provided before ordering for a site can take place. The dose order will be a direct order from the study site to the Sponsor who shall arrange appropriate supply of IMP. The coordinating CRO will also be in copy of the order (please refer to the IMP Handling Manual for details). Upon establishment of patient eligibility (see Section 4.2), the clinical site manager will order individualised doses of Zr-TLX250 solution for IV administration, via the Sponsor for direct delivery to the study site. A dose can be cancelled at any time however if the cancellation is less than 2 days prior to administration date then the site will need to follow IMP handling manual for appropriate disposal of product. Zr-TLX250 for IV administration will be provided by Telix International Pty Ltd and used unchanged from the original state. The treating investigator at the site will delegate ordering of Zr-TLX250 solution for IV administration to the clinical site manager, overseeing eligibility and planned treatment dates, for direct delivery to the site to the attention of the radiopharmacist.

